## 5.2.1.2. Generalized Marginal Model for Repeated Measures (GMMRM)

As a supportive analysis of ACR50, scheduled to be collected multiple times during the first 3 months of the placebo-controlled period (Week 2, Months 1, 2 and 3) of the study, a generalized marginal linear model for repeated measures (GMMRM) will be used. This model will have fixed effects for time (discrete), treatment, and time by treatment interaction; the dependent variable will be logit of the probability of response. Note that the model includes fixed effects of treatment, visit, and treatment-by-visit interaction only to ensure the estimated response rates and the treatment difference have a population average or marginal interpretation. A common AR(1) variance-covariance matrix for both treatment sequences will be used to model the variability among observations within a subject. If AR(1) matrix fails to converge, compound symmetry will be attempted. The parameters of the model will be estimated with pseudo-likelihood type methods. Simulations investigating generalized linear models (GLM) for correlated binary data indicate good performance as measured by type I error, confidence interval coverage and bias even in the presence of data that is MAR (Liu and Zhan, 2011).

From this model, one can obtain estimate of the probability of response for each treatment sequence at each timepoint as well inferential comparisons (odds ratio, CI and p-value) between treatment sequences.

In the event that a response rate is 0 or 100% at a particular visit for a treatment sequence that may lead to convergence issues, data from that visit for both treatment sequences will be removed from the model fitting in order to overcome any numerical difficulty.

## 5.2.1.3. Tipping Point Analysis

A method to analyze the longitudinal binary data measured during the placebo-controlled period at Week 2, Months 1, 2 and 3 under the missing not at random (MNAR) assumption is called the tipping point analysis. This analysis is used as a supportive analysis for the primary endpoint of ACR50 at Month 3. It assesses the robustness of the binary data to potential deviations from the missing at random (MAR) assumption for both tofacitinib 5 mg BID and placebo groups and it is based on multiple imputation (Yan, Lee and Li, 2009; Ratitch, O'Kelly and Tosiello, 2013).

In this tipping point analysis, a single saturated generalized linear mixed effect model is used as the imputation model. The normal approximation of the difference in binomial proportions is used for the analysis, which is the same as the method of analyzing response-type endpoint at a single time point described in Section 5.2.1.1. The generalized linear mixed effect model includes the fixed effects of treatment, visit, treatment-by-visit interaction, and a latent subject-level random effect. The logit link is used to model the ACR50 response rate as dependent variable for all visits. Estimation of the model parameters is performed under the Bayesian framework using Markov chain Monte Carlo (MCMC) methods. Only the available data without imputation are included in this generalized linear mixed effect model to estimate the model parameters.

Imputation of missing ACR50 response is performed only at Month 3 based on the predictive distribution of the generalized linear mixed effect model. Under missing not at random (MNAR) assumption, a fixed MNAR quantity (favorable or unfavorable) will be applied to the probability of the ACR50 response at Month 3 for subjects with missing response in the tofacitinib 5 mg BID group and placebo group independently (i.e., the analysis will be two-dimensional applied to both tofacitinib 5 mg BID and placebo). A series of fixed quantities will be applied to the probability of the ACR50 response at Month 3 for subjects with missing response in the tofacitinib 5 mg BID group or placebo group independently to assess when the conclusion might change (i.e., tipping). A scenario included in the tipping point analysis framework is an analysis under MAR, if there is no fixed quantity applied to the mean of the missing response for subjects in the tofacitinib 5 mg BID group and placebo group. The Rubin's rules (Rubin, 1987) will be used to combine the results of multiple imputed samples for inference. More detailed descriptions are provided in Appendix 4.

## 5.2.2. Analyses for Continuous Data

Continuous endpoints will be analyzed by Mixed Model Repeated Measures (MMRM) that includes the fixed effects of treatment, visit, treatment by visit interaction, and baseline value. An unstructured variance covariance matrix for within-subject correlation (an alternative variance covariance matrix will be used if the model does not converge under the unstructured variance covariance matrix). Comparison of the two treatment sequences at each post-baseline timepoint will be generated from this model (providing 2-sided p-values and 95% CI).

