#### 9.1. Sample Size Determination

The sample size and power analysis for the primary endpoint are based on the randomization of approximately 204 subjects in a 2:1 ratio. The sample size for this study is driven by the ACR50 response rate.

Assuming a placebo response rate of 9.5% and factoring in the number of subjects with primary endpoint missing due to COVID-19 (around 11 subjects as of 29 May 2020), a sample size of approximately 204 Chinese subjects (approximately 136 subjects in the tofacitinib treatment arm and 68 subjects in the placebo arm) randomized in a 2:1 ratio to tofacitinib and placebo arms will yield at least 90% power to detect a difference of 18.5% from placebo in ACR50 response rate, based on normal approximation (without continuity correction) at the 2-sided 5% significance level.

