#### 9.2.2. Analysis of Secondary Endpoints

Binary endpoints will be analyzed similarly as for the primary analysis of ACR50.

The  $\Delta$ HAQ-DI will be analyzed using a repeated measure model that includes the fixed effects of treatment, visit (Week 2, Months 1, 2, 3, 4 and 6), treatment by visit interaction, and baseline value, and an unstructured variance covariance matrix for within-subject correlation (an alternative variance covariance matrix will be used if the model does not converge under the unstructured variance covariance matrix). Other continuous endpoints will be analyzed similarly.

Details of the analysis methods for all the endpoints will be enumerated in the SAP.

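### The repeated-measures model fixes one baseline slope for all visits; if that slope changes over time, Month 3 precision for the continuous endpoints falls somewhat, and one added term avoids it.

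*SAP*

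**What the plan says.** SAP 5.2.2 defines the model for every continuous endpoint as one that "includes the fixed effects of treatment, visit, treatment by visit interaction, and baseline value", with an unstructured within-subject covariance and a fallback structure if that fails to converge. Protocol 9.2.2 gives the same list for change in HAQ-DI, ending in "treatment by visit interaction, and baseline value", and extends it to the other continuous endpoints. SAP Appendix 1 repeats the four terms for each endpoint. None of the three places has a baseline-by-visit term.

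The number of visits in each model comes from SAP 6.2.2, 6.3 and Appendix 1:

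- Six visits (Week 2 and Months 1, 2, 3, 4 and 6): the seven ACR components, including HAQ-DI, and DAS28-3(CRP).
- Three visits (Months 1, 3 and 6): PGA-PsO, DSS, LEI, SF-36, EQ-5D, PGA-PsA, PASI, BSA and NAPSI.
- Two visits (Months 3 and 6): WPAI-PsA.

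SAP 5.1 says that the study is not powered for endpoints other than ACR50 at Month 3 and that their intervals and p-values are nominal.

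**The concern.** Each visit has its own treatment effect and its own variance, but all visits share one baseline coefficient. If baseline predicts Week 2 better than it predicts Month 3, no single coefficient fits both. The fitted value is a weighted average. When the baseline correlation decays and the SD stays stable, the early visits carry most of the weight. In the six- and three-visit models, data from after the Month 3 placebo switch also help to set the slope used for the placebo-controlled Month 3 contrast.

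What is at stake is the width of the Month 3 intervals. Protocol 1.2.6 says the study is meant to support a claim that includes improved physical function, and change in HAQ-DI at Month 3 is the continuous measure closest to that claim.

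**Working it through.** **The plan's own figure.** The only precision figure in the documents is for ACR50: the sample size "will yield at least 90% power to detect a difference of 18.5% from placebo in ACR50 response rate", "based on normal approximation (without continuity correction"). With 9.5% v 28.0% and 68 v 136 subjects, the unpooled standard error used by the SAP 5.2.1.1 test is √(0.28×0.72/136 + 0.095×0.905/68) = 0.0524. Power is Φ(0.185/0.0524 − 1.96) = 94.2%. Counting 11 of 204 subjects as non-responders gives 92.6%. The stated figure reproduces, and it does not involve the repeated-measures model. No SD, visit correlation or baseline slope is given for any continuous endpoint.

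**Formula.** Scale the baseline SD to 1. With equal SDs and baseline correlation ρ_t at visit t, the baseline slope for change is b_t = ρ_t − 1 and the residual variance is 1 − ρ_t². The generalised-least-squares common slope is b* = Σ w_t b_t, where the weights are the row sums of the inverse residual covariance, scaled to add to 1. With complete data, the Month 3 variance inflation is (b_M3 − b*)² / residual variance at Month 3.

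**Worked case (assumed pattern).** Let the correlation between two visits d months apart be 0.85·exp(−0.15d), with Week 2 at 0.5 month.

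- The slopes at the six visits are −0.21, −0.27, −0.37, −0.46, −0.53 and −0.65.
- The weights are 0.46, 0.22, 0.08, 0.05, 0.05 and 0.14, so Week 2 and Month 1 carry 68% and Month 3 carries 5%.
- b* = −0.328 and b_M3 = −0.458, a gap of 0.130.
- Residual variance at Month 3 is 1 − 0.542² = 0.706.
- Inflation is 0.130²/0.706 = 2.4% of variance, or 1.2% of standard error.

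**Range.** Correlation is r0·exp(−a·d). In each cell the first figure is for equal SDs and the second for an SD falling by up to 25%.

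| r0, a | Six visits, Month 3 variance | Three visits, Month 3 variance |
|---|---|---|
| 0.4-0.8, 0 (constant) | 0% / 0% | 0% / 0% |
| 0.80, 0.03 | 0.1% / 0.5% | 0.0% / 0.1% |
| 0.80, 0.08 | 0.7% / 1.4% | 0.1% / 0.3% |
| 0.85, 0.15 | 2.4% / 3.5% | 0.7% / 0.8% |
| 0.90, 0.20 | 4.5% / 6.1% | 1.3% / 1.4% |

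A further set of assumed patterns gave 5-9% for six visits under steep decay and up to 3% for three visits. For WPAI-PsA, Month 3 is itself the first visit in the model, so no earlier visit can dominate.

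**Simulation at 136:68** (400 runs per scenario, six visits). The ratio of model-based Month 3 variance, common slope to visit-specific slopes, was 1.000, 1.007 and 1.026 with complete data (constant, moderate and steep decay). With about 9% missing-at-random dropout by Month 3 it was 1.000, 1.011 and 1.036. The mean treatment estimates of the two models agreed within 0.002 throughout.

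**HAQ-DI scale.** Protocol 1.2.2 reports −0.35 v −0.18 with P=0.0062 in the global pivotal study. That implies z = 2.737 and a standard error of 0.17/2.737 = 0.0621. Assume arms of 107 and 105, inferred from 28.04% = 30/107 and 9.52% = 10/105. The residual SD is then 0.0621/√(1/107 + 1/105) = 0.452.

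Here the standard error would be 0.452×√(1/136 + 1/68) = 0.0672, with power 71.6% for a difference of 0.17. At 6% inflation, power is about 69%. At 9%, the standard error is 0.0672×√1.09 = 0.0701 and power is Φ(0.17/0.0701 − 1.96), about 68%. A 9% inflation equals losing 204×(1 − 1/1.09), about 17 subjects, for that endpoint.

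**The case against.** The strongest reply is that this is a modelling preference. Three places in the documents agree on a pre-specified, baseline-adjusted model with unstructured covariance. The only decision rule, ACR50 at Month 3, does not use it, nor do the HAQ-DI responder endpoints. Any loss works against the sponsor and does not raise false positives. No correlation is documented, so the loss cannot be shown to exist. All of that stands. It limits the point to a minor improvement, but it does not remove a possible gain that is almost free.

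A reader might infer more, in four ways that the documents do not support:

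- **That precision is certainly lost, over six visits, for every continuous endpoint.** The loss is conditional and is zero with a constant slope. Among the secondary endpoints, only the ACR components have six visits.
- **That the loss is large.** Assuming that the baseline correlation falls much faster than the correlation between follow-up visits can push the inflation to 27% or more. Nothing in the documents supports so extreme a pattern.
- **That the treatment effect is biased.** In the worked case, a chance baseline imbalance of one standard error shifts the Month 3 estimate by 0.130/√0.706, about 0.15 standard errors. With complete data, such shifts average to zero over randomisations, and simulated dropout changed the mean estimates by no more than 0.002.
- **That the physical-function claim is at risk.** Protocol 1.2.6 names physical function, but the plan attaches no success criterion to change in HAQ-DI.

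**Conclusion.** The point holds as a minor one. The model imposes a common baseline slope on all visits, and no reason is given. If the slope changes over time, Month 3 variance is inflated by roughly 0-9% (0-4% of standard error) in six-visit models and 0-3% in three-visit models; with a constant slope the inflation is 0%. These are results under assumed correlations, mostly smooth exponential decay with SDs constant or falling by up to 25%. They are not bounds and not estimates for this trial. The treatment effect is unbiased on average, the primary analysis is untouched, and the affected intervals and p-values are nominal.

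**What to change.** Add a baseline-by-visit interaction to the fixed effects in SAP 5.2.2 and in each mixed-model row of Appendix 1, before unblinding. This costs five extra parameters in six-visit models, two in three-visit models and one for WPAI-PsA, with about 204 subjects randomized (fewer in the endpoint-specific subsets). It uses only data already collected. If the slopes prove constant, almost nothing is lost.

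The opening of Protocol Section 9 allows the SAP to modify planned analyses and requires an amendment only for major changes to the primary endpoint or its analysis. Protocol 9.2.2 therefore need not be amended; a line in the SAP version history noting the difference is enough. If the sponsor prefers to keep the current model as the main one, the version with the interaction can be pre-specified as a sensitivity analysis.

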## 5.2.3. Analyses of Tier-2 Adverse Events

Number and percentage of subjects with AEs over the first 3 months will be provided for each treatment group. Tier-2 events will be analyzed using asymptotic methods proposed by Miettinen and Nurminen (1985). Risk ratios (tofacitinib 5mg BID compared to placebo) and 2-sided 95% CI will be reported. P-values will not be reported for Tier-2 events.

#### 5.3. Methods to Manage Missing Data

As stated in the protocol, in the primary analysis of the primary endpoint, ACR50 response rate at Month 3, missing values for any reason, e.g., due to a subject dropping from the study or due to the impact of COVID-19 pandemic, will be handled by setting the ACR50 value to nonresponsive. Note that this can be viewed as a composite endpoint in the sense that a response requires the subject completes a visit of interest, e.g., Month 3, and achieves a response per the defined ACR50 response criteria (otherwise it is considered a nonresponse). This method of handling missing response is known as missing response as non-response (MR=NR). This MR=NR approach will be used for all "response-type" endpoints at all timepoints except for the supportive analyses using GMMRM (see Section 5.2.1.2) and Tipping Point Analysis (see Section 5.2.1.3) for ACR50 up to Month 3. Note that if a subject

discontinues from the study at a visit of interest, say Month 3, but the value of the endpoint is not missing at Month 3, the value of the endpoint will be used for Month 3.

For a composite "response-type" endpoints (such as ACR50), if values in any of the components at a timepoint are missing, the component variables that are not missing will be used to determine the response status. If one could not determine the response status in the presence of missing components at the timepoint, then the composite response-type endpoint status is considered as missing and is handled by MR=NR for that timepoint for all of the inferential analyses except for the supportive analyses using GMMRM (see Section 5.2.1.2) and Tipping Point Analysis (see Section 5.2.1.3) for ACR50 up to Month 3.

Repeated measures data for continuous and ordered-categorical (analyzed as continuous) endpoints will be analyzed with MMRM. This model will yield unbiased estimates and valid inferences in the presence of data that is MCAR or missing at random (MAR). Given that subjects who drop out are scheduled to have an end of study evaluation, the more stringent condition of MAR (Rubin, 1987) is believed to be a reasonable assumption. Hence missing values will not be imputed in the routine analysis using the repeated measures model.

For the SF-36, EQ-5D and WPAI-PsA instruments, rules suggested by the developers of these will be followed in calculating scores when individual question/items may be missing. If these rules are not enough for calculating a score, then the endpoint will be considered to have a missing value, and this missing value will be addressed as specified in the paragraph above.

In general, missing values in any of the endpoints will not be imputed when summarizing these endpoints using descriptive statistics.

For the demographic and baseline characteristics, if a value is missing, a missing category will be added to summaries for the categorical variables.

Missing values for safety endpoints will not be imputed.

#### 6. ANALYSES AND SUMMARIES

6.1. Primary Endpoint(s)

#### 6.1.1. ACR50 Response Rate at Month 3

6.1.1.1. Primary Analysis

Endpoint: ACR50 response rate at Month 3

- Analysis time points: Month 3
- Analysis population: FAS

- Method of imputation for missing data: MR=NR (specified in Section 5.3)
- Analysis methodology: The normal approximation to the difference in binomial proportions (specified in Section 5.2.1.1) will be used to test the difference between tofacitinib 5 mg BID and placebo and to generate 95% CI and p-value for the difference in response rates.

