# 4.5. Randomization Criteria

A subject who has signed an informed consent document to participate in the study, has undergone all screening procedures, and meets all inclusion and no Exclusion Criteria for participation in the study at the baseline visit, may be randomized into this study. Subjects will be randomized in a 2:1 ratio to one of the two parallel treatment sequences. A centralized computer-generated randomization schedule will be used to assign subjects to the treatment groups. Subjects will be assigned a subject identification number in the order of their screening for the study. The identifying number will be retained throughout the study.

At Month 3, subjects originally randomized to Treatment Sequence B will be advanced to tofacitinib 5 mg BID treatment in a blinded fashion for the remainder of the study. Study blinding will be maintained for all groups throughout the study (see Section 6.2).

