## 9.2. Efficacy Analysis

## 9.2.1. Analysis of Primary Endpoint of ACR50 Response Rate

The normal approximation to the difference in binomial proportions will be used to test the difference between tofacitinib 5 mg BID and placebo and to generate 95% confidence interval for the difference in response rates.

Missing values for any reason, eg, due to a subject dropping from the study or due to the impact of COVID-19 pandemic will be handled by setting the ACR50 value to nonresponsive. The SAP will also specify additional analyses to assess the sensitivity of the primary analysis to departures from the assumed missing data mechanism.

The analysis will include all randomized subjects who receive at least 1 dose of study drug.

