## 2.2. Study Design

This is a Phase 3, randomized, 6-month, double-blind, placebo-controlled, parallel-group study designed to evaluate the efficacy and safety of tofacitinib in adult, Chinese subjects with active PsA who had an inadequate response in their PsA to at least one csDMARD. All subjects in the study will be evaluated for risk factors for venous thromboembolism. A total of approximately 204 subjects will be randomized in a 2:1 ratio to one of the following two parallel treatment sequences. The enrollment will be monitored to cap the proportion of subjects with baseline swollen joint count  $\leq 5$  at approximately 38% (i.e., approximately 78 subjects).

A schematic of the study design is shown in Figure 1.

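### No ACR50 analysis, primary or supportive, adjusts for a baseline covariate; prespecifying a standardised rate difference would be a cheap and modest improvement to a plan that is otherwise sound on this point

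*SAP*

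**What the plan says.** **Primary analysis.** Protocol 9.2.1 states: "The normal approximation to the difference in binomial proportions will be used to test the difference between tofacitinib 5 mg BID and placebo". SAP 6.1.1.1 repeats this: "The normal approximation to the difference in binomial proportions (specified in Section 5.2.1.1) will be used to test the difference". SAP 5.2.1.1 gives the statistic: the raw difference in proportions over its unpooled standard error. The analysis uses the full analysis set (FAS), with missing response counted as non-response (MR=NR). No covariate or stratum appears.

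**Randomization.** Protocol 4.5 says: "A centralized computer-generated randomization schedule will be used to assign subjects to the treatment groups". Protocol 5.1 describes a 2:1 schedule from which each subject takes the next entry. Neither section names a stratification factor.

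**Swollen joint count.** SAP 2.2 says: "The enrollment will be monitored to cap the proportion of subjects with baseline swollen joint count" of 5 or fewer, at about 38%, or about 78 subjects. The count is summarised at baseline (SAP 3.4.2). It enters no ACR50 model and is not a subgroup in SAP 6.4. The nearest subgroup there splits at 5 joints that are swollen or tender, which is a different variable.

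**Supportive ACR50 analyses.** The per-protocol analysis (SAP 6.1.1.2) and the COVID-19 analysis (SAP 6.7.1) repeat the unadjusted test on other sets. The repeated-measures model (SAP 5.2.1.2) and the tipping-point imputation model (SAP 5.2.1.3, Appendix 4) have treatment, visit and their interaction as the only fixed effects. For the repeated-measures model alone, the SAP gives a reason: to keep a population-average interpretation.

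**Continuous endpoints.** These are adjusted for their baseline value (SAP 5.2.2).

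**The concern.** The trial controls the overall share of subjects with few swollen joints but takes no described step to balance that share between arms. A cap fixes the mix in the whole trial and does nothing for the comparison. If the baseline table shows a visible difference between arms, the plan offers no prespecified adjusted estimate, and any later adjustment would be post hoc.

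The comparison rests on few events. At the planning rate, 68 × 0.095 gives about 6 placebo responders. Baseline data already in hand could reduce the variance of the estimate if they predict response. They could also remove the part of the observed difference that comes from imbalance in those factors. A standardised rate difference estimates the same marginal quantity as the planned analysis, so the reason given in SAP 5.2.1.2 does not stand in the way.

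**Working it through.** **1. Inputs.** From Protocol 9.1: placebo rate 9.5%; power "to detect a difference of 18.5% from placebo in ACR50 response rate", so 28.0% on tofacitinib; "approximately 136 subjects in the tofacitinib treatment arm and 68 subjects in the placebo arm"; testing "at the 2-sided 5% significance level"; about 11 subjects with the endpoint missing because of COVID-19, split by arm not given. From SAP 2.2: about 78 of 204 subjects with swollen joint count ≤5. The documents do not say how strongly any baseline factor predicts ACR50, so all prognostic strengths below are assumptions.

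**2. Stated power, unadjusted.** With the SAP 5.2.1.1 statistic:

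- No missing data: SE = √(0.28×0.72/136 + 0.095×0.905/68) = 0.0524, and power = Φ(0.185/0.0524 − 1.96) = 94.2%.
- The 11 removed (193 analysed): 93.0%.
- The 11 as non-responders in proportion to arm size: rates are multiplied by 193/204 to give 26.5% and 9.0%, SE = 0.0513, and power = Φ(0.175/0.0513 − 1.96) = 92.6%.

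The figure of at least 90% is reproduced. Simulation of the third case gives 90.8% to 90.9%. Two caveats apply. A pooled-variance formula gives 86.7% to 89.2% for the same three cases, but it is not the SAP's statistic. The result also depends on where the 11 fall: with 10 or all 11 in the tofacitinib arm, unpooled power is 89.5% or 88.1%.

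**3. Adjusting for swollen joint count ≤5 alone.** Simulation with 100,000 trials per setting; variance of the stratum-standardised difference relative to unadjusted:

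| Assumed odds ratio | 1 | 1.5 | 2 | 3 | 5 |
|---|---|---|---|---|---|
| Variance ratio | 1.005 | 1.002 | 0.992 | 0.969 | 0.931 |

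**4. Adjusting for three covariates.** Logistic g-computation with swollen joint count, CRP and prior bDMARD experience; 4,000 trials per setting; rates 26.5% vs 9.0%. The prevalences are 38% (the cap), 50% and 20%; the last two are assumed.

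| Odds ratios (joints, CRP, bDMARD) | Variance ratio | Power, unadjusted → adjusted |
|---|---|---|
| 1, 1, 1 | 1.01 | 90.9% → 90.9% |
| 1.5, 1.5, 1.5 | 1.00 | 90.8% → 90.8% |
| 2, 2, 0.5 | 0.98 | 90.5% → 91.6% |
| 3, 2, 0.5 | 0.96 | 91.7% → 93.0% |
| 3, 3, 0.33 | 0.93 | 91.8% → 93.7% |

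With 9% in both arms, rejection was 5.6% to 6.5% unadjusted and 5.4% to 6.5% adjusted. Both run slightly above 5%, and adjustment neither causes nor cures that. A model with swollen joint count and CRP only should fall between steps 3 and 4.

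**5. Chance imbalance.** With f = 78/204 = 0.382, the SD of the between-arm difference in the ≤5 share is √(0.382×0.618×(1/136 + 1/68)) = 0.072. That is 7.2 points, with a 95% range of about ±14 points. The shift in the estimate is this imbalance times the response difference between strata:

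| Assumed difference between strata | Shift at 1 SD | Shift at 1.96 SD |
|---|---|---|
| 10 points | 0.7 points | 1.4 points |
| 20 points | 1.4 points | 2.8 points |

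The half-width of the 95% confidence interval is 1.96 × 0.0513 to 1.96 × 0.0524, or about 10 points.

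**The case against.** The case for leaving the plan alone is substantial, and most of it stands.

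- **The planned test is coherent.** Sample size, protocol analysis and SAP analysis all use the same unadjusted normal approximation. Chance imbalance does not bias the difference over repeated randomizations and is already reflected in its standard error.
- **A reader might infer from the cap that swollen joint count is a known prognostic factor.** The documents never say so. The only reason given, in the protocol's document history, is to keep the population similar to the global study A3921091. CRP and bDMARD experience appear only as subgroups for checking consistency.
- **A reader might also infer that precision is certainly being lost.** That needs a prognostic strength the documents do not supply. With no association the variance rises by about 1%, and at odds ratios of 1.5 to 2 the gain is very small.
- **Adjustment is not free of risk.** Protocol 1.2 notes that no TNF inhibitor is approved for this disease in China, so the bDMARD-experienced stratum may be small. With about 6 placebo responders, extreme coefficients appeared in 0.2% to 5% of simulated three-covariate fits under the design alternative, and in up to about 30% in the sparsest null setting.
- **Some imbalance would be visible anyway**, through the baseline tables and the SAP 6.4 forest plots.

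What this does not answer is that visibility is not correction. No planned ACR50 analysis would show how the result changes after allowing for a baseline difference.

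**Conclusion.** The concern holds as a modest, low-cost improvement. The plan contains no covariate-adjusted ACR50 analysis and describes no stratification, while suitable baseline data are collected in every subject. The unadjusted test remains valid and meets its stated power, given the SAP's unpooled statistic and a proportional split of the 11 missing subjects.

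For assumed odds ratios of 1 to 3 per covariate (or the inverse for bDMARD experience), the variance changes by about +1% to -7% and power rises by about 0 to 2 points. The correction for imbalance in swollen joint count would typically be about 0.7 to 1.4 points, if response differs by 10 to 20 points between strata. That is small beside a half-width of about 10 points. Neither gain is needed to justify the trial's size. The stronger benefit is having an agreed answer before unblinding if the arms differ at baseline.

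**What to change.** Before unblinding, prespecify a covariate-standardised (g-computation) difference in Month 3 ACR50 rates on the FAS with MR=NR:

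- Use a logistic model with treatment, baseline swollen joint count and baseline CRP (≤2.87 vs >2.87 mg/L), with a robust variance.
- Add prior bDMARD experience only if that stratum is large enough, judged on blinded data.
- State a fallback for separation or non-convergence: drop the sparse covariate or use penalised logistic regression.
- Report the result beside the unadjusted difference. At minimum it belongs in SAP 6.1.1.2 as a supportive analysis. Making it the primary estimate would also need a protocol amendment, under the rule in Protocol 9 and SAP 2.
- Add swollen joint count ≤5 vs >5 to the SAP 6.4 subgroups.

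The cost is SAP text and a little programming, with no new data and no extra subjects. The statistical downside is a variance loss of about 1% if the covariates turn out not to be prognostic.
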